Clinical Trial Protocol

Physiologic Phacofluidics: Ghost Protocol

Protocol Number: 83557125

Principal Investigator: [name] PHD
Address Wolfe Eye Clinic
[name]
[name]

[contact]

IRB: Advarra

This protocol is confidential and the information available within it may not be reproduced or otherwise disseminated.

Physiologic Phacofluidics: Ghost Protocol

Protocol V4.0

Date: 9/30/2023

Purpose: To investigate the early post-operative clinical benefits when performing phacoemulsification at physiological intraocular pressure (IOP) using Centurion® Vision System with Active Sentry® handpiece

Background: Phacoemulsification and intracapsular lens implantation is the most common performed eye surgery to correct vision loss and restore vision for patients with cataract. During phacoemulsification, the ocular environment changes because of the heat generated by dissipated ultrasound energy, high perfusion, fluctuation in intraocular pressure (IOP), and the inflammatory response resulting from surgical manipulation.

Historically, the advances of phacoemulsification cataract surgery technologies have been geared towards increased efficiency of cataract removal, decreasing intra-operative complications, and faster post-operative visual recovery. A long-standing dogma of phacofluidics has been that high non-physiologic IOP settings (>65 mm Hg) are required for highly efficient cataract extraction. However, studies are showing that operating at lower IOPs levels are as safe and efficacious¹; and "physiological phaco" between 20-30mmHg may yield additional intra-operative and post-operative benefits:

- The lack of significant and rapid pressurization changes will result in significantly less early corneal edema in after cataract surgery²
- The normotensive intra-operative environment is gentler on the corneal endothelium resulting in clearer and healthier corneas in the short and long term; Some suggest that an increase in central corneal thickness (CCT) on the first postoperative day correlates with surgical trauma to the endothelium and that it is proportional to cell loss at 3 months³
- The Active Sentry (AS) Handpiece can maintain anterior chamber stability at low IOP settings, thus providing added safety and a gentler intra-operative environment^{1,4}
- Elicit a lower post-operative inflammatory response²

Several studies have looked at inflammatory indicators in FLACS (femtosecond laser-assisted cataract surgery)^{8,9}.

There has been minimal research on the clinical benefits in early post-op (initial hours after surgery) care and no studies evaluating inflammatory response in early post-operative stages with cataract surgery performed at near physiological IOP.

As cataract surgeons ever strive towards matching the speed of recovery and accuracy of visual outcomes of our corneal refractive counterparts, near physiologic phacoemulsification with the safety of the Centurion Active Sentry handpiece combined with low IOP phacoemulsification settings will likely be a key technological step forward towards that goal.

Methods:

Study population

Inclusion Criteria

- Patients without prior ocular surgery both eyes
- Adult patients with visually significant cataract with WHO-World Health Organization NUC grade 2-3
- First eye only undergoing uncomplicated cataract surgery
- Unremarkable systemic history; controlled diabetes with HbA1c <7%
- Unremarkable ocular health
- Anterior chamber depth ACD >2.04mm¹⁰
- Age range 55-95

Exclusion Criteria:

- Prior ocular surgery including corneal refractive surgery, cataract surgery in fellow eye
- Thin corneas (<490 microns)
- Complicated (use of pupil expansion devices) or prolonged cataract surgeries (>15 mins) with post-operative complications (IOP spike >30mmHg), severe punctate keratitis

Approximately 66 patients will be identified and included in the study. Patients at the day of surgery sign up will be randomized to high (65mmHg) vs low IOP (20mmHg) using a random online number generator; Even will be high IOP; Odd will be low IOP. Patients will undergo standard cataract surgery with equivalent vacuum and aspiration rates in both groups for the duration of the entire cataract surgery; IOP settings will be set at high vs low IOP but may be adjusted if necessary for the safety of the patient.

In all procedures, the intraocular lens (IOL) implanted and the ophthalmic viscosurgical device (OVD) materials used will be standardized to the same materials and are part of routine surgery. Cumulative dissipated energy (CDE) and surgical duration will be collected for all patients. An intraoperative aqueous sample 100-150µL will be collected at the end of the case 2 minutes after OVD removal and immediately transferred on dry ice to a laboratory, stored at -80°C until analysis as established in prior protocol.⁶ The extraction of aqueous sample will not require additional incisions.

All subjects will be prescribed the standard post-operative cataract surgery medications (not specific to study). Post-operative visits by the masked sub-investigator will perform the following procedures at 4hrs (early post-op), POD#1 (20-24hrs), POW#1:

Post-op Procedures	Baseline	Visit1 (4hrs)	Visit2 (20-24hrs)	Visit3 (1 week)
Pachymetry	X	X	X	X
Visual acuity	BCVA	UCVA/PHVA	UCVA/PHVA	UCVA/PHVA
Slit Lamp- Cell /Flare	X	X	X	X

Pachymetry: a painless, simple test where a probe is gently placed on the front of the eye to measure the thickness of the cornea.

Best-corrected visual acuity (BCVA): this test is used to determine the smallest letters that can be read on a standardized chart. Un-corrected visual acuity (UCVA): the smallest letter that can be read unaided. Pinhole visual acuity (PHVA): the smallest letter that can be read without the interference of optical problems.

Slit lamp exam: a microscope is used to provide a magnified view of different parts of the eye and to determine inflammation (cell/flare) that is common with any ophthalmic surgery.

Visual acuity and slit lamp examinations are part of routine post-operative care. Pachymetry measurements are for research purposes to determine if there's less corneal swelling after cataract surgery in the lower IOP group.

The primary end point is: difference in CCT post-op at 4 hours between High vs Low IOP groups. Secondary endpoints include: CCT at POD#1 and POW#1, Cell/Flare at POHr4 and POD1, and inflammatory markers: levels of prostaglandin IL-6, IL-8, IL-1 β , TNF- α , PGE2, MCP-1. Aqueous samples will be sent with de-identified patient information and aqueous analysis will be performed by the University of California, Irvine Molecular Biology and Biochemistry Labs. The laboratory will be masked to which treatment the subject received and will only provide the aqueous analysis report for the study.

Any adverse events (AE) will be recorded in subject's medical charts as well as an adverse event log. AEs are classified as serious or non-serious; expected or unexpected; and study-related, possibly study-related, or not study-related. Serious AEs will be reported immediately to the regulatory authorities as per standard of care. The potential risks involved are that of standard cataract surgery with potential complications and side effects associated with any surgical procedure. These include but are not limited to: infection, macular edema, increased IOP, general risk of anesthesia and surgery, bleeding in the eye, and decreased vision. Some potential benefits include: improved visual acuity, decreased glare symptoms, lowered IOP, and faster visual recovery.

Analysis:

Primary endpoint: Difference in mean CCT change at 4 hrs post-surgery between high vs low IOP will be assessed using t-test with a P-value <0.05. Descriptive statistics will be used for the other secondary endpoints

Sample Size Justification:

In Vasavada et al²., the expected mean CCT change between the high vs low groups is hypothesized to be 32um, with a standard deviation of 40um. With a Type I/II error rate of alpha=0.05 and power=0.85, a sample size of 56 eyes are needed; additional 10 eyes to account for ~15 attrition; N=66

Data Collection and Management:

Data is recorded in a manner that reduces the risk of a breach of confidentiality. Password protected Microsoft Excel files will be utilized for this study and only accessible by authorized study personnel.

Ethical and Regulatory Considerations:

The study is conducted in accordance with the following:

Protocol and study-related plans and documents

- Local regulations, as applicable
- Good Clinical Practices, as outlined in the ICH Harmonized Tripartite Guideline for GCP (ICH)

E6(R2))Ethical and Regulatory Considerations:

The study is conducted in accordance with the following:

- Protocol and study-related plans and documents
- Local regulations, as applicable
- Good Clinical Practices, as outlined in the ICH Harmonized Tripartite Guideline for CP (ICH)
- The ethical principles established by the Declaration of Helsinki
- Regional participant data protection laws and regulations
- Local IRB requirements

Institutional Review Board (IRB):

The study site will maintain an accurate and complete record of all reports, documents and other submissions made to the Institutional Review Board (IRB) concerning this protocol.

The investigator must supply ongoing study progress reports to the IRB, per local requirements, protocol deviations and amendments. In addition, the investigator must notify the IRB at the closure of the study.

Informed Consent:

It is the responsibility of the investigator and clinical coordinator to inform each subject of the purpose of this study, including possible risks and benefits and document the informed consent process in the subject's chart. Prior to entry into the study or initiation of any study-related testing, the subject must read, sign and date the informed consent form. If the subject's vision is impaired to the point where they cannot read the informed consent document, the document will be read to the subject. The person executing the consent must also sign and date the consent form. One original informed consent form is to be retained by the study site and a copy is to be given to the subject.

Protocol Amendments:

This protocol must be followed as written. Any change or addition to this protocol that impacts subject safety, or the validity of the study requires a written protocol

amendment that must be approved in writing by the IRB and any required regulatory authorities before implementation.

Record Keeping and Retention:

Data generated for the study should be stored in a limited-access file area and be accessible only to study personnel of the site. All reports and communications relating to study participants will identify participants only by subject identification number. Complete subject identification will be kept by the investigator. This information will be treated with strict adherence to professional standards of confidentiality.

The Investigator will retain a copy in the study file:

- A copy of the IRB approved informed consent form
- All original informed consent forms with required signatures
- All participant source documents, etc.
- All IRB correspondence (i.e., informed consent [including any approved revisions], protocol, AE, advertisements, newsletters).

Confidentiality:

All clinical study findings and documents are regarded as confidential. Study documents (protocols and other material) must be stored appropriately to ensure their confidentiality.

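### NUC grade (2 or 3) is known before randomisation but is left out of the primary 4-hour CCT comparison; adjusting for it is a cheap precision gain, not the repair of an invalid test

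*Combined protocol and SAP*

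**What the plan says.** In the combined protocol and SAP, the Inclusion Criteria under Methods admit "Adult patients with visually significant cataract with WHO-World Health Organization NUC grade 2-3". Nuclear grade is not mentioned again.

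Allocation, described in the paragraph after the Exclusion Criteria, is made "using a random online number generator; Even will be high IOP; Odd will be low IOP". No strata, blocks or minimisation are stated.

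The Analysis section gives the primary comparison: "Difference in mean CCT change at 4 hrs post-surgery between high vs low IOP will be assessed using t-test with a P-value <0.05". It names no covariate.

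The Background says that during phacoemulsification "the ocular environment changes because of the heat generated by dissipated ultrasound energy", among other causes. Methods has CDE and surgical duration recorded for every patient, but states no use for either in the primary analysis.

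**The concern.** An entry criterion has to be settled before a patient is allocated, so the site will hold a grade for every eye at the time of the draw. Harder nuclei generally need more ultrasound energy. That is general surgical knowledge and is not stated in the documents, although the Background does name ultrasound energy as a source of change in the eye. If grade predicts corneal swelling at 4 hours, leaving it out has two costs. The difference between grades stays in the error term, and in a trial of this size one arm may by chance receive noticeably more grade 3 eyes, with no pre-specified analysis to account for it.

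CDE and duration cannot fill this gap. Both are measured after the assigned IOP setting is applied and may be affected by it, so adjusting for them could remove part of the treatment effect. Grade is fixed beforehand.

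**Working it through.** **Inputs from the documents.** The Sample Size Justification supplies the effect and spread: "the expected mean CCT change between the high vs low groups is hypothesized to be 32um, with a standard deviation of 40um". From a 5% alpha and 85% power it arrives at 56 evaluable eyes, then adds 10 for attrition to reach 66. The test is taken as two-sided because sidedness is not stated. The attrition figure is read as 15%.

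**Assumed, because the documents give no value.** The share p of grade 3 eyes is 0.3 to 0.5. The extra 4-hour CCT change g in grade 3 over grade 2 eyes is 0 to 30 um. The SD of 40 um is a total SD that already contains any grade effect.

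**1. The plan's own figures.** n per arm = 2 x [40 x (1.960 + 1.036) / 32]^2 = 28.06, or 56.1 in total, which matches 56. A one-sided test would need 23 per arm and does not match. Attrition: 56 / 0.85 = 65.9, which matches 66. Exact t-test power at 28/28 is 83.6%, close to the stated 85%.

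**2. Validity of the unadjusted test.** In simulations of 56 eyes allocated by parity, the type I error of the t-test stays at about 5% for every g examined, and the estimated difference is unbiased on average.

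**3. Chance imbalance.** The arms differ by 20 or more percentage points in grade 3 share in about 10-14% of trials (lower end p = 0.3, upper end p = 0.5). A 20-point imbalance shifts that trial's estimate by 0.20 x g:
- g = 15: 0.20 x 15 = 3 um
- g = 30: 0.20 x 30 = 6 um

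The shift can go in either direction. The standard error at 28/28 is 40 x sqrt(2/28) = 10.7 um, so it amounts to 3/10.7 = 0.3 to 6/10.7 = 0.6 of a standard error, or 3/32 = 9% to 6/32 = 19% of the target difference.

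**4. Residual SD after adjustment.** Residual SD = sqrt(1600 - p(1-p)g^2).
- g = 15, p = 0.3: sqrt(1600 - 0.21 x 225) = 39.4 um
- g = 30, p = 0.5: sqrt(1600 - 0.25 x 900) = 37.1 um

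**5. Power with grade in the model, existing draw unchanged.** Simulated for 56 eyes, true difference 32 um, p = 0.3 to 0.5. Unadjusted power is about 83% throughout, slightly below 83.6% because a parity draw leaves the arms uneven in size.

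| Assumed grade effect g | Power adjusted for grade |
|---|---|
| 0-5 um | about 82% |
| 10 um | about 83% |
| 15 um | about 83.5% |
| 20 um | about 84-84.5% |
| 30 um | about 87-87.6% |

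These figures include the lost degree of freedom and the chance imbalance of the draw. Putting the smaller residual SD into the power formula at 28/28 gives 84.7-88.7% for g = 15-30 um, but that presumes grades perfectly balanced between arms, which the even/odd draw does not provide.

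**The case against.** The strongest reply is that an unadjusted t-test after simple randomisation is a legitimate primary analysis, and that its standard error already allows for chance imbalance. This stands. A reader might infer that an excess of grade 3 eyes in one arm would be mistaken for an IOP effect and so invalidate the result. Step 2 does not support that: the error rate holds, and the estimate is not biased over randomisations. The 3-6 um shift describes a single realised trial and is well under one standard error.

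Second, the link from grade to CCT change is undocumented, and 30 um for one grade step would nearly equal the whole 32 um effect expected between the IOP arms. This also stands, and it is why effects down to zero are shown.

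Third, the plan already limits variation. It admits only two adjacent grades, excludes complicated or prolonged surgery, standardises the lens and viscoelastic, keeps vacuum and aspiration equivalent, and analyses change in CCT. These steps make a large residual grade effect less likely but do not rule one out.

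The reply does not remove the case for using a baseline value that the trial must obtain anyway. The trial is run once, and with visibly unequal grades its readers would have no pre-specified adjustment to turn to.

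**Conclusion.** The omission is real, its consequence is probably modest, and the remedy is cheap. Over assumed grade effects of 15-30 um, adjustment under the existing draw adds from about half a point to between 4 and 5 points of power. At 10 um or less it adds nothing, and it costs just under one point at worst. All of this rests on the assumed grade mix and grade effect and on 40 um being a total SD.

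Two stronger readings are not supported. A reader might infer that the sample size is wrong, but 56 and 66 reproduce, and a total SD already contains grade variance if the source population had a similar mix. A reader might also expect adjustment alone to bring power to 85-89%; that needs balanced grades.

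**What to change.** Record NUC grade (2 or 3) on the enrolment form before the draw. Before any results by arm are seen, pre-specify the primary comparison as a linear model of 4-hour CCT change with terms for arm and grade (2 versus 3), tested at the planned 0.05 level. Keep the unadjusted t-test as a sensitivity analysis, and report grade by arm at baseline. State that CDE and surgical duration will not be used as adjusting variables in this comparison.

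Stratifying the draw by grade is optional and adds little once grade is in the model, so the change does not depend on altering the randomisation.

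The cost is one analysis sentence, one form field the site needs for eligibility anyway, one degree of freedom, and under one point of power if grade turns out not to predict CCT change. No patients or procedures are added.

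### Eyes can be excluded for events seen only during or after the randomised surgery, and no analysis set says whether they stay in the primary comparison

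*Combined protocol and SAP*

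**What the plan says.** Under Methods, Study population, the timing of allocation is clear: "Patients at the day of surgery sign up will be randomized to high (65mmHg) vs low IOP (20mmHg". The Exclusion Criteria in the same section include "Complicated (use of pupil expansion devices) or prolonged cataract surgeries (>15 mins) with post-operative complications (IOP spike >30mmHg), severe punctate keratitis", and the Inclusion Criteria require "First eye only undergoing uncomplicated cataract surgery". The randomisation paragraph allows departures from the assigned setting: "IOP settings will be set at high vs low IOP but may be adjusted if necessary for the safety of the patient". It also states that "Cumulative dissipated energy (CDE) and surgical duration will be collected for all patients".

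The Analysis section gives one sentence on the primary endpoint: a t-test at the 0.05 level of mean CCT change at 4 hours, high against low IOP. It names no intention-to-treat, modified or per-protocol set. It has no rule for eyes that meet an exclusion after allocation, eyes whose setting was adjusted, or eyes with no 4-hour CCT. The Sample Size Justification adds 10 eyes for attrition without saying whether these exclusions count as attrition. The Publication section asks for review of complete data, but that defines no analysis population.

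**The concern.** An eligibility rule applied after randomisation can undo the randomisation if the events it uses depend on treatment and relate to the outcome. Both are plausible here; neither is shown.

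- **Dependence on treatment.** The Background reports the long-held view that high pressure settings "are required for highly efficient cataract extraction", so the setting could affect surgery time. It then says newer studies find lower settings as safe and efficacious, so this is only a possibility. Nothing links use of a pupil device to the setting.
- **Relation to the outcome.** The Background cites a suggestion that early CCT increase reflects surgical trauma. Long or complicated cases could therefore swell more.
- **Who influences the events.** The post-operative assessor is masked ("Post-operative visits by the masked sub-investigator will perform the following procedures") and so is the laboratory ("The laboratory will be masked to which treatment the subject received"). No text masks the surgeon, whose decisions bear on duration.
- **Detection.** The visit table schedules no IOP measurement, so when a spike would be found is not stated.

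The bias could go either way. If more low-IOP cases run long and are dropped, low IOP looks better than it is. If more high-IOP eyes have complications and are dropped, a real benefit shrinks. Two analysts following this protocol could test different sets of eyes, and the choice could be made after CCT is known.

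**Working it through.** **1. Is any exclusion necessarily post-randomisation?** The criterion can be read as separate items, or as prolonged surgery together with post-operative complications. Keratitis may be meant as a baseline condition, need for a pupil device may sometimes be foreseen, and uncomplicated may mean expected to be so. On every reading at least one element (duration over 15 minutes, or a post-operative spike) is observed only after allocation.

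**2. The plan's own sample size.** Inputs from the Sample Size Justification: difference 32 µm, SD 40 µm, alpha 0.05 (two-sided reproduces the figure; one-sided gives 46), power 0.85.

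n per arm = 2 × [40 × (1.960 + 1.036) / 32]² = 28.06, or 56.1 in total, which matches 56. Then 56 / 0.85 = 65.9, which matches 66. Power of the t-test itself (noncentral t) is 83.6% at 28 per arm and 89.3% at 33 per arm. The arithmetic is not the problem.

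**3. Bias if the eyes are dropped, with no true effect.** Assume a latent exclusion risk that has correlation ρ with CCT change, and drop the fraction p of eyes at highest risk in each arm. With c = z(1 − p) and λ(p) = φ(c)/(1 − p), the bias in high minus low is

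40 × ρ × [λ(p_low) − λ(p_high)].

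For 20% low and 10% high: λ(0.20) = 0.350 and λ(0.10) = 0.195. At ρ = 0.5, 40 × 0.5 × (0.350 − 0.195) = 3.1 µm. Type I error comes from simulation (33 per arm before exclusion, pooled two-sided t-test, 40,000 trials per cell).

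| Excluded, low vs high | Expected eyes of 33 | Bias, µm, ρ = 0.3 / 0.5 / 0.7 | Type I error, % |
|---|---|---|---|
| 8% vs 2% | 2.6 vs 0.7 | 1.3 / 2.2 / 3.1 | 5.2 / 5.4 / 6.1 |
| 18% vs 12% | 5.9 vs 4.0 | 1.1 / 1.9 / 2.6 | 5.0 / 5.4 / 5.7 |
| 20% vs 10% | 6.6 vs 3.3 | 1.9 / 3.1 / 4.3 | 5.3 / 5.9 / 7.3 |
| 25% vs 5% (severe) | 8.3 vs 1.7 | 3.8 / 6.3 / 8.8 | 6.3 / 9.2 / 13.9 |

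Equal rates acting alike give zero. Equal rates acting differently do not: with ρ = 0.7 in the low arm and 0.3 in the high arm, the bias is 40 × 0.4 × λ(p), which is 1.7 µm at 5% each and 4.4 µm at 15% each.

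**4. The other direction, true difference 32 µm and more exclusions in the high arm.**

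| Excluded, high vs low | Mean estimate, µm, ρ = 0.3 / 0.5 / 0.7 | Power, % |
|---|---|---|
| None | 32 | 89 |
| 15% vs 15% | 32.0 at each ρ | 85 / 87 / 90 |
| 8% vs 2% | 30.7 / 29.7 / 28.9 | 86 / 84 / 84 |
| 20% vs 10% | 30.1 / 28.9 / 27.7 | 80 / 79 / 80 |
| 25% vs 5% (severe) | 28.2 / 25.8 / 23.2 | 74 / 69 / 63 |

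Part of each fall in power is plain loss of eyes, as the balanced row shows.

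**5. A simpler cross-check.** If event eyes have a fixed excess CCT change, the shift is (low event rate − high event rate) × excess. With 15% low, 5% high and an excess of 20, 40 or 80 µm, it is 2, 4 or 8 µm. The simulated rejection rate under no effect is then about 5%, 6% or 12%. Reversing the rates reverses the sign.

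**The case against.** The strongest reply is that no text says these eyes leave the t-test. The Analysis section compares high with low IOP and duration is recorded for everyone, so what is proven is an undefined population, not a planned biased one. The wording may reach few eyes if the conditions are joint. Entry is restricted to nuclear grade 2–3, unremarkable ocular health and a minimum chamber depth, and vacuum and aspiration are held equivalent; all this may make events rarer or more alike between arms. Every rate above is assumed. Outside the severe case, for which the documents offer no support, the differential-rate scenarios put bias at no more than 4.3 µm against a planned 32 µm and type I error at no more than 7.3%.

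Most of this stands as a limit on size. It does not remove the defect. Eyes on an exclusion list would naturally be taken out, and nothing says otherwise. Taking them out selects on events after allocation, whichever reading is used. Surgeon masking, the missing IOP measurement and setting adjustments are related matters that the calculations do not model, and they add nothing to the figures. It is also fair that a set requiring a 4-hour CCT still depends on that measurement being obtained, so missing values need their own rule.

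**Conclusion.** The concern holds. At least one stated exclusion can be known only after randomisation, and no analysis set says how such eyes are treated. The population for the trial's only planned test is therefore open, and the natural reading of the exclusion list would break the randomised comparison.

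The size cannot be derived from the documents. Under moderate assumed splits the bias is roughly 1 to 4 µm, with type I error of about 5% to 7%. Larger distortion needs a severe split between arms. There is no bias if exclusions are balanced and act alike in both arms. The case for correction rests on the population being undefined and the direction of bias unpredictable, not on a large expected bias. It should be settled before outcomes are seen.

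**What to change.** 1. Clarify the criterion: are the items separate or joint, and is keratitis a baseline condition?
2. Limit eligibility to facts known before randomisation.
3. Define the primary set as every randomised eye that has surgery and a 4-hour CCT, analysed in its assigned arm whatever the duration, complications or setting adjustment. Report eyes without a 4-hour CCT by arm with reasons, and state how they are handled.
4. Report by arm the duration, device use, setting adjustments and recorded complications, with IOP spikes where IOP is measured in routine care or logged as an adverse event.
5. Keep the uncomplicated-cases set as a labelled sensitivity analysis, with counts removed per arm.

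The cost is a wording amendment and one extra analysis. No patients or procedures are added, because duration and adverse events are already recorded. The downside is that retained complicated eyes may add variance. If the SD rose from 40 to 42 or 44 µm (assumed), power at 33 per arm would be 86% or 83% instead of 89%. Losing 5 eyes per arm at SD 40 gives 84%, so keeping the eyes costs about the same as dropping them, or less, and preserves the randomisation.

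### A post-operative IOP spike is listed as an exclusion after randomisation, with no scheduled IOP measurement behind it; keep those eyes in the 4-hour CCT analysis and report spikes by arm

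*Combined protocol and SAP*

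**What the plan says.** The last bullet of Exclusion Criteria concerns complicated or prolonged surgeries "with post-operative complications (IOP spike >30mmHg), severe punctate keratitis". The next paragraph of Methods places randomisation on the day of surgery, to an intra-operative setting of 65 or 20 mmHg.

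The masked sub-investigator "will perform the following procedures at 4hrs (early post-op), POD#1 (20-24hrs), POW#1". The Post-op Procedures table has three rows: pachymetry, visual acuity, and slit lamp for cell and flare. The text below it states that "Visual acuity and slit lamp examinations are part of routine post-operative care" and that pachymetry is done for research. IOP measurement is not mentioned.

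The primary endpoint is CCT at 4 hours. "Secondary endpoints include: CCT at POD#1 and POW#1, Cell/Flare at POHr4 and POD1, and inflammatory markers"; IOP is not among them. The adverse event paragraph lists "infection, macular edema, increased IOP, general risk of anesthesia and surgery" among the risks and "improved visual acuity, decreased glare symptoms, lowered IOP, and faster visual recovery" among the benefits. On capture it says "Any adverse events (AE) will be recorded in subject's medical charts as well as an adverse event log". The Analysis section specifies a t-test on CCT change and does not say which randomised eyes enter it.

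**The concern.** Two features of the rule work together.

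- **It acts after randomisation.** An exclusion on a post-operative event cannot be a screening rule. Its practical effect would be to remove an eye that has already been allocated and operated on, for an event the allocation may influence. The two arms are then no longer the groups that randomisation produced.
- **Its ascertainment is not specified.** No visit provides the IOP value that the rule needs. If pressure is checked in some eyes and not others, a swollen cornea is a plausible prompt, and corneal swelling is what the primary endpoint measures. Masking the examiner limits checking driven by knowledge of the arm. It does not limit checking driven by the look of the cornea, which the trial expects to differ between arms.

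At stake are the primary comparison, if removals differ between arms, and the quality of the post-operative IOP safety data in a trial whose randomised factor is intra-operative IOP.

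**Working it through.** **1. The plan's own figures.** Sample Size Justification gives a difference of 32 µm, SD 40 µm, alpha 0.05 and power 0.85. Two-sided, with equal arms and the normal approximation:

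n per arm = 2 × (1.960 + 1.036)² × (40/32)² = 2 × 8.98 × 1.5625 ≈ 28.1

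This is 56 in total at 28 per arm (power 0.849), or 58 if rounded up. The stated 56 is reproduced to within rounding. With 15% attrition, 56/0.85 = 65.9, so 66. The 10-eye allowance is the only reserve for all losses, including any removals under this rule. At these planning values t-test power is 0.893 with 66 eyes and 0.836 with 56.

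**2. Is an IOP value specified anywhere?**

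| Place | Content | IOP measured? |
|---|---|---|
| Exclusion Criteria | Spike above 30 mmHg | Needed, no source given |
| Post-op Procedures table | Pachymetry, acuity, slit lamp | No |
| Test descriptions | Thickness, letters read, inflammation | No |
| Endpoints | CCT, cell/flare, aqueous markers | No |
| Adverse events | Chart and log | No method or time point |
| Analysis | t-test on CCT change | No |

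**3. Effect of removal on an arm mean (illustration; every input assumed).** Suppose a fraction f of an arm is removed and those eyes average 40 µm (one planning SD) above the full arm mean. The mean of the remaining eyes shifts by −40 × f/(1 − f).

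| f | Shift | Share of 32 µm |
|---|---|---|
| 5% | −40 × 0.05/0.95 = −2.1 µm | 7% |
| 10% | −40 × 0.10/0.90 = −4.4 µm | 14% |
| 15% | −40 × 0.15/0.85 = −7.1 µm | 22% |

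These rows assume removal in one arm only, the extreme case. With 10% removed in one arm and 5% in the other, the net shift is 4.4 − 2.1 = 2.3 µm (7% of 32 µm). With equal fractions and equal excess it is zero.

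For scale, the standard error of the difference at 28 per arm is 40 × √(2/28) = 10.7 µm, so 2.3 µm is about 0.2 and 7.1 µm about 0.7 of a standard error.

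**4. Direction.** The high-IOP arm is expected to swell more. Removing swollen eyes from it shrinks the difference (at f = 10%, 32 − 4.4 = 27.6 µm). Removing them from the low-IOP arm inflates it (32 + 4.4 = 36.4 µm).

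**5. Incomplete checking (assumed rates).** With a spike rate of 2% to 15% and 25% to 50% of eyes checked, expected detections among 66 eyes run from 66 × 0.02 × 0.25 = 0.3 to 66 × 0.15 × 0.50 = 5.0. Expected misses run from 66 × 0.02 × 0.50 = 0.7 to 66 × 0.15 × 0.75 = 7.4.

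**The case against.** The strongest reply is that this is a drafting gap and not a demonstrated threat to the result. Several parts of it stand.

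- **The criterion may be narrow.** Read literally, a spike counts only when surgery was already complicated or prolonged, so few eyes might be affected. A reader might infer that any spike above 30 mmHg removes an eye; the text does not settle that. Both readings still need an IOP value and still act after randomisation.
- **Silence is not absence.** A reader might infer that pressure would be checked only when someone chose to. The sentence on routine care sorts the listed tests into routine and research; it does not claim to list all usual care. A routine IOP check is neither established nor excluded, so the supportable word is unspecified.
- **Spikes could still be reported.** A reader might infer that IOP safety by arm cannot be reported at all. Spikes that reach the adverse event log could be tabulated by arm, though not systematically. Nor does naming a risk by itself require a test: macular edema is in the same list with no dedicated test scheduled.
- **Measurement alone does not cure the bias.** If the rule stayed, measuring every eye could lead to more removals. Once all eyes are retained, missing IOP data no longer touch the primary comparison.
- **Safety information would be modest.** With 33 eyes per arm, zero spikes leaves a one-sided 95% upper bound of 1 − 0.05^(1/33) = 8.7%.

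None of this reconciles the criterion with the schedule or justifies removing randomised eyes from the CCT analysis.

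**Conclusion.** The point holds as a should-fix. A post-operative event that the randomised setting could affect is listed as an exclusion, its scope is ambiguous, and the schedule specifies no measurement with which to apply it. Removing eyes on that rule can bias the 4-hour CCT difference in either direction, depending on which arm loses more swollen eyes.

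The size is unknown. Under the stated assumptions it runs from zero (equal removal), through about 2.3 µm (10% versus 5%), to 7.1 µm (15% from one arm only), set against a planned 32 µm. The upper figure should not be read as an estimate: the one-SD excess, the removal rates and the imbalance are all assumed. The documents do not show that the primary result would be overturned. The bias arises from removal after randomisation; the missing IOP row mainly affects how even-handed the safety report can be.

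**What to change.** 1. Reconcile the exclusion criterion with the visit schedule, and state whether the spike wording stands alone or applies only to complicated or prolonged surgery.
2. State in Analysis that every randomised eye with a CCT reading enters the primary comparison in its allocated arm, whether or not a spike occurs.
3. Report IOP spikes by arm as a safety outcome, using the plan's own 30 mmHg figure, instead of treating them as a reason for removal.
4. To support that report, record IOP in every eye at the existing 4-hour, day 1 and week 1 visits, by the same masked examiner and after pachymetry so that the primary reading is not disturbed.

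Items 1 to 3 need only text changes, and item 2 is the one that protects the primary result. Item 4 adds a brief measurement and one data field, with no new visit or staff; if IOP is already taken in usual care, only the recording is new. The whole change fits in one amendment, with the IRB approval that Protocol Amendments requires. It should be made before further eyes are treated, because an unrecorded 4-hour pressure cannot be recovered later.
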